6.2.1.1. Dose Modifications for Hematological Toxicities

Recommendations for dose modification due to study drug-related hematologic toxicities are presented in [Table 9](#).

Table 9: Recommendations for Management of Hematologic Toxicities

Grade by CTCAE v5.0	Management Recommendation
Grade 1 and 2	No dose modifications required
Anemia and Thrombocytopenia	
Grade 3	Suspend TAS3351 until resolved to Grade ≤ 2 or baseline, then: 
 • If resolved ≤ 14 days, resume at the same dose level • If resolved > 14 days or re-occurrence, resume at next lower dose level
Grade 4	Suspend until resolved to Grade ≤ 2 or baseline, then resume at next lower dose level
Neutropenia (ANC)	
Grade 3 lasting ≤ 3 days	No dose modifications required
Grade 3 lasting > 3 days or Grade 4	Suspend TAS3351 until resolved to Grade ≤ 2 or baseline, then 
 • If resolved ≤ 7 days, resume at the same dose level • If resolved > 7 days or re-occurrence, resume at next lower dose level
Febrile neutropenia	Suspend TAS3351 until resolved, then resume at next lower dose level

Abbreviations: ANC=absolute neutrophil count; CTCAE=Common Toxicity Criteria for Adverse Events

6.2.1.2. Dose Modifications for Non-hematologic Toxicities

Recommendations for dose modification due to study drug-related diarrhea, hepatic events, skin rash, QT prolongation, interstitial lung diseases (ILD), and other non-hematologic toxicities are presented in [Table 10](#).

Table 10: Recommendations for Managing Non-Hematologic Toxicities

Grade by CTCAE v5.0	Management Recommendation
Diarrhea (see also Section 6.4.4.2)	
Grade 1 and 2	No dose modifications required, initiate supportive therapy (see Section 6.4.4.2) If persistent / recurrent Grade 2 that does not resolve with maximal supportive measures, reduce to next lower dose level
Grade 3	Suspend dose until resolved to \leq Grade 2, then: 
 • If resolved ≤ 14 days, resume at the same dose level and consider anti-diarrheal prophylaxis • If resolved > 14 days or re-occurrence, resume at next lower dose level
Grade 4	Suspend dose until resolved to \leq Grade 1 or baseline, then resume at next lower dose level.
Hepatic events	
Bilirubin increased	
Grade 1 and 2	No dose modifications required Note: Assess AST and ALT for \geq Grade 2 bilirubin (see Hy's law below)
Grade 3	Suspend dose until resolved to \leq Grade 1 or baseline, then: 
 • If resolved ≤ 14 days, resume at the same dose level • If resolved > 14 days or re-occurrence, resume at the next lower dose level
Grade 4	Discontinue study drug
AST or ALT increase	
Grade 1 and 2	No dose modifications required NOTE: Assess bilirubin for \geq Grade 2 AST/ALT (see Hy's law below)
Grade 3	Suspend dose until resolved to \leq Grade 1 (\leq Grade 2 in the presence of liver metastasis) or baseline, then: 
 • If resolved ≤ 14 days, resume at the same dose level • If resolved > 14 days, resume at the next lower dose level
Grade 4	Discontinue study drug
Hy's law	
AST or ALT $> 3.0 \times \text{ULN}$ with bilirubin $> 2.0 \times \text{ULN}$	Discontinue study drug, except: 
 • Other reason found to explain the findings (such as viral hepatitis A, B, or C, pre-existing or acute liver disease, or another drug capable of causing the observed liver injury) or • Initial findings of cholestasis (elevated serum ALP)

Grade by CTCAE v5.0	Management Recommendation
Skin Rash	
Grade 1 and 2	No dose modifications required Topical steroid (eg, hydrocortisone 2.5%) and clindamycin cream BID, as needed, and consider oral antibiotic (eg, doxycycline 100 mg BID) for 2 to 4 weeks
Grade ≥ 3	Suspend dose until resolved to \leq Grade 2 and manage as shown above for Grade 1/2 considering additional oral steroids, then: 
 • If resolved ≤ 14 days, resume at the same dose level and consider prophylactic management of skin rash • If resolved > 14 days or re-occurrence, resume at next lower dose level
QT prolongation	
Grade 1	
 • Repeat ECG (triplicates, 2-3 minutes apart) • If QTcF is still on average > 450 ms, check electrolytes and replace to maintain $K \geq 4.0$ mmol/L, $Mg \geq 1.8$ mg/dL (0.9 mmol/L) and $Ca > 8.0$ mg/dL (2.0 mmol/L) and repeat ECG • No dose modifications required
Grade 2	
For first occurrence:
 
 • Repeat ECG (triplicates, 2-3 minutes apart) • Check electrolytes and replace to maintain $K \geq 4.0$ mmol/L, $Mg \geq 1.8$ mg/dL (0.9 mmol/L) and $Ca > 8.0$ mg/dL (2.0 mmol/L) and repeat ECG • If QTcF is still on average > 481 ms, suspend drug until resolved to \leq Grade 1, and then resume at the same dose level 
If re-occurrence:
 
 - Suspend drug until resolved to \leq Grade 1 and then resume at the next lower dose level
Grade 3	
 • Repeat ECG (triplicates, 2-3 minutes apart) • Check electrolytes and replace to maintain $K \geq 4.0$ mmol/L, $Mg \geq 1.8$ mg/dL (0.9 mmol/L) and $Ca > 8.0$ mg/dL (2.0 mmol/L) and repeat ECG • If QTcF is still > 500 ms and/or > 60 ms change from baseline, suspend drug until resolved to \leqGrade 1 and obtain an evaluation by a cardiologist. If study drug can be resumed, it should be at the next lower dose level • If re-occurrence, consider discontinuing the study drug
Grade 4	Discontinue study drug

Grade by CTCAE v5.0	Management Recommendation
Interstitial Lung Disease (ILD) / Pneumonitis (see also Section 6.4.4.3)	
Grade 1	No dose modifications required, consider follow-up at regular intervals as per institutional standards
Grade 2	Suspend dose until resolved to \leq Grade 1, then: 
 • If resolved \leq14 days, maintain dose level • If resolved $>$14 days, resume at the next lower dose level If clinical symptoms persist/worsen despite treatment, consider discontinuing study drug
Grade 3 and 4	Discontinue study drug
Corneal ulceration	
Grade \geq 3	Discontinue study drug
Other Non-hematologic Toxicities	
Grade 1 and Grade 2	No dose modifications required, administer supportive therapy as indicated
Grade 3	Suspend dose until resolved to \leq Grade 1 or baseline (\leq Grade 2 for toxicities that are manageable by supportive therapy, such as asymptomatic electrolyte changes, dyspepsia, hypertension), then: 
 • If resolved \leq14 days, resume at the same dose level • If resolved $>$14 days or re-occurrence, resume at next lower dose level
Grade 4	Suspend dose until resolved to \leq Grade 1 or baseline, then resume at next lower dose level. Discontinue study drug if re-occurrence or occurrence of an irreversible treatment related clinically significant event.

Abbreviations: ALP=alkaline phosphatase; ALT=alanine aminotransferase; AST=aspartate aminotransferase; BID=twice daily; CTCAE=Common Terminology Criteria for Adverse Events; ECG=electrocardiogram; QD=once daily; QTc=corrected QT interval; QTcF=Fridericia's Correction Formula for corrected QT interval; T-bil=total bilirubin; ULN=upper limit of normal.

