2.2.1.6. QT Prolongation

Human ether-a-go-go related gene (hERG) current inhibition was detected with an IC₅₀ value of 860 nmol/L TAS3351, and a dog telemetry study revealed a non-dose proportional QT-prolongation at 10-40 mg/kg at a single time point. Therefore, TAS3351 has a potential to induce QT prolongation.

Patients with pre-existing increased QTc interval, cardiac comorbidity(ies), and any other risks associated with QT prolongation will be excluded per study protocol. Patients will have an ECG assessment at baseline and during treatment. Electrolytes will be monitored, and imbalance should be corrected.

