6.2. Dose and Schedule Modifications

The following general dose modification guidelines for patients receiving TAS3351 should be followed:

- Supportive treatment for any AE should be optimized before any modification is considered.
- If the symptoms of AE promptly resolve with supportive care, consideration should be given to continuing study drug along with appropriate continuing supportive care.

Recommended dose modifications are based on the occurrence of treatment-related AEs and are provided for hematological toxicities (Section 6.2.1.1) and non-hematological toxicities (Section 6.2.1.2). If an Investigator suspends treatment or reduces doses without one of the dose reduction, interruption and resumption criteria being met, this is acceptable and would not be considered a protocol deviation.

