Echocardiography/MUGA	Baseline echocardiography/MUGA (multi-gated acquisition scan) is required. Left ventricular ejection fraction (LVEF) monitoring is needed every 4 cycles during TAS3351 treatment, and as clinically indicated. LVEF can be assessed by ECHO or MUGA; same modality should be used for a patient at screening and after dosing. See Section 7.1.3.
Hematology	Red blood cell (RBC) count, hemoglobin, hematocrit, platelets, white blood cell (WBC) count with differential: neutrophils (ANC), lymphocytes, monocytes, eosinophils, basophils. See Section 7.1.4.
Serum chemistry	AST, ALT, ALP, total bilirubin, direct bilirubin, albumin, LDH, triglyceride, total cholesterol, creatinine, BUN, Na, K, Cl, Ca (corrected value), Mg, blood glucose, C reactive protein (CRP), lipase, amylase, creatinine clearance (if there is a measured value, use the measured value) or eGFR. See Section 7.1.4. For a calculated CrCl value, use the Cockcroft-Gault formula: Male: $\text{CrCl} = \frac{(140 - [\text{insert age in years}] \times [\text{insert weight in kg}])}{72 \times [\text{insert serum creatinine in mg/dL}]}$ Female: $\text{CrCl} = \frac{(140 - [\text{insert age in years}] \times [\text{insert weight in kg}])}{72 \times [\text{insert serum creatinine in mg/dL}]} \times 0.85$
Coagulation	PT-INR, APTT, and fibrinogen. See Section 7.1.4 .
Urinalysis	Urine protein (qualitative), sediment, occult blood by dipstick or laboratory. If urine protein is 2+, add urinary β 2-microglobulin and quantitative measurement of proteinuria (24-hour urine collection for protein preferred). See Section 7.1.4.
Pregnancy test	For all female patients of childbearing potential: Serum or urine human chorionic gonadotrophin (human chorionic stimulating hormone) test (see the local regulation and/or CTFG recommendations). For screening, serum test required.
ECOG performance status	See Oken et al. for details. ²⁷
Efficacy and other	
Efficacy assessments	Efficacy assessment by tumor imaging. See Section 7.1.1.
Survival follow-up	Patient or family should be contacted for survival follow-up until withdrawal of consent, death, or loss to follow-up, until study completion. This should also include further anti-cancer treatments administered.
PK blood sampling	See Section 8.1 and Laboratory Manual.
Pharmacodynamic biomarker sampling	See Section 11.

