10.2. Laboratory Assessments

See [Table 12](#) for the list of clinical laboratory assessments to be performed and the Schedule of Events ([Table 1](#) and [Table 2](#)) for timing and frequency.

All laboratory assessments will be performed locally. The laboratory must provide normal reference ranges for hematology, chemistry, urine, and coagulation tests. If justified (eg, deterioration of the patient's health conditions and/or distance from the clinical site) and permitted by the country and institution, laboratory tests performed by external laboratories may be used for the study. However, laboratory reference ranges and accreditation are required.

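### Table 10's magnesium replacement target for QT prolongation pairs 1.8 mg/dL with 0.9 mmol/L, which are different concentrations

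*Protocol*

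**What the plan says.** Protocol Section 6.2.1.2, Table 10, sets out how to manage QT prolongation by grade. In the Grade 1, Grade 2 (first occurrence) and Grade 3 rows, sites repeat the ECG, check electrolytes, and replace them to stated targets before a further ECG. The magnesium and calcium targets read "Mg \geq 1.8$ mg/dL (0.9 mmol/L) and $Ca > 8.0$ mg/dL (2.0 mmol/L) and repeat ECG". Potassium has a target in mmol/L only.

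What follows depends on QTcF, not on magnesium. For a first Grade 2 occurrence the rule is "If QTcF is still on average > 481 ms, suspend drug until resolved" to Grade 1 or lower. For Grade 3, suspension depends on QTcF still above 500 ms and/or more than 60 ms above baseline. Grade 1 needs no dose change. The Grade 2 re-occurrence and Grade 4 instructions contain no magnesium step.

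Other relevant places:

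- Protocol Section 2.2.1.6 describes the QT risk and names electrolyte control among the safeguards: "Electrolytes will be monitored, and imbalance should be corrected". It gives no threshold.
- Protocol Table 12 (Section 7.1) lists the chemistry panel, "Na, K, Cl, Ca (corrected value), Mg, blood glucose", with no unit or limit for magnesium. SAP Table 8 does the same.
- Protocol Section 10.2: "All laboratory assessments will be performed locally".
- Protocol Section 5.1 sets a numeric eligibility limit for potassium and none for magnesium.

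**The concern.** A figure in one unit followed by a bracketed figure in another should be a single target expressed twice. Here the bracket appears to hold a different target. If so, the instruction has two answers, and a site cannot tell from the documents which one governs.

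The step belongs to the management of a named risk. TAS3351 inhibited hERG with an IC50 of 860 nmol/L, prolonged QT in dog telemetry, and has no prior human experience. The protocol also anticipates vomiting and diarrhea, with electrolyte imbalance in severe cases (Section 2.2.1.1). In two of the three rows (first Grade 2 occurrence and Grade 3), replacement comes before the repeat ECG that informs the decision to suspend. A patient with magnesium between the two figures could therefore reach that ECG either supplemented or not, depending on which figure was read.

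**Working it through.** **Inputs.** From Table 10: magnesium 1.8 mg/dL with 0.9 mmol/L in brackets; calcium 8.0 mg/dL with 2.0 mmol/L in brackets. From outside the documents, as physical constants: molar mass of magnesium 24.305 g/mol and of calcium 40.078 g/mol.

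**Formula.** mmol/L = (mg/dL × 10) / molar mass, and mg/dL = (mmol/L × molar mass) / 10.

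**Control: the calcium pair on the same line.** 8.0 × 10 / 40.078 = 1.996 mmol/L, which agrees with the printed 2.0. The bracket is therefore meant as a unit equivalent, and the formula reproduces the protocol's own figure.

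**Magnesium.**

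- 1.8 × 10 / 24.305 = 0.741 mmol/L; the protocol prints 0.9.
- 0.9 × 24.305 / 10 = 2.187 mg/dL; the protocol prints 1.8.
- Gap: 0.900 − 0.741 = 0.159 mmol/L, or 2.187 − 1.800 = 0.387 mg/dL.
- Ratio: 0.9 / 0.741 = 1.215, so the bracketed figure is about 22% above the true equivalent.

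**Could rounding explain it?**

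| Printed figure | Values that round to it | In the other unit |
|---|---|---|
| 1.8 mg/dL | 1.75 to 1.85 mg/dL | 0.720 to 0.761 mmol/L |
| 0.9 mmol/L | 0.85 to 0.95 mmol/L | 2.07 to 2.31 mg/dL |

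The highest value that rounds to 1.8 mg/dL is 0.761 mmol/L, and the lowest that rounds to 0.9 mmol/L is 0.85. The ranges do not overlap.

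**Could text extraction explain it?** The same pair appears in three separate rows, next to a calcium pair that is correct. A repeated identical misreading is implausible.

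**A possible source.** Magnesium is divalent, so 0.9 mmol/L is 2 × 0.9 = 1.8 mEq/L. The pair would be right if the first unit were mEq/L, so mg/dL may have been written in its place. This is an inference. The documents do not say so, and it does not establish which concentration was intended.

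**What each reading implies for a patient with QT prolongation:**

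| Serum magnesium | Target read as 1.8 mg/dL | Target read as 0.9 mmol/L |
|---|---|---|
| Below 0.74 mmol/L | Replace | Replace |
| 0.74 to just under 0.90 mmol/L | Do not replace | Replace |
| 0.90 mmol/L or above | Do not replace | Do not replace |

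Only the middle band is affected. The documents do not allow an estimate of how many patients would fall in it.

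**The case against.** The arithmetic is not open to dispute; the argument on the other side is about weight.

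1. **Limited effect.** Magnesium triggers no hold, reduction or discontinuation. The ECG repeats, the QTcF criteria and the potassium and calcium targets stand whichever figure is used. The section describes its content as "Recommendations for dose modification due to study drug-related diarrhea, hepatic events, skin rash, QT prolongation" and other toxicities, so it advises rather than mandates. All of this stands, and it limits how serious the point is. The allowance in Section 6.2 that departing from the criteria "this is acceptable and would not be considered a protocol deviation" covers suspending or reducing the dose. It does not address electrolyte replacement and does not help either side.

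2. **One target with a faulty bracket.** The inequality sign is attached to the mg/dL figure, "Mg \geq 1.8$ mg/dL (0.9 mmol/L", so a reader could take that as the instruction and the bracket as a slip. This is a natural reading but not a secure one. If the unit of the leading figure is the mistake, as the mEq/L match suggests it could be, the bracket is the correct part. A site whose laboratory reports in mmol/L would in any case go straight to the bracket.

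3. **Differences between sites are not shown.** Laboratories are local, but the protocol does not state their reporting units. This is fair: divergence requires sites to report in different units or to read the line differently. The SAP's demographics section lists eight countries (five for Part A1, three more from Part A2), and nothing in the plan ensures a common unit, so the possibility is open. It remains a possibility.

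**Conclusion.** The two magnesium figures in Table 10 are different concentrations, 0.16 mmol/L (0.39 mg/dL) apart, and nothing else in the Protocol or SAP says which one applies. The mismatch is printed in three rows; in two of them the replacement step precedes a QTcF-based decision to suspend. The conversion rests only on the molar mass of magnesium.

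The clinical consequence is confined to patients with QT prolongation whose magnesium lies between 0.74 and 0.90 mmol/L, and their number is unknown. Sample size, error rates, endpoints and analyses are untouched. The point should be corrected because it is an action threshold in the safety management of an identified cardiac risk in a first-in-human trial, and the correction is simple.

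**What to change.** The sponsor's clinical team should decide the intended concentration and print one matching pair in the Grade 1, Grade 2 (first occurrence) and Grade 3 QT rows of Table 10:

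- **If the lower target is intended:** Mg ≥ 1.8 mg/dL (0.74 mmol/L).
- **If the higher target is intended:** Mg ≥ 2.2 mg/dL (0.9 mmol/L). Check: 2.2 × 10 / 24.305 = 0.905 mmol/L. This is the same concentration as 1.8 mEq/L, should the sponsor prefer that unit.

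Send sites a short clarification stating the chosen value and make the text change at the next amendment. The cost is one corrected figure in three table rows plus the clarification. No new data, procedures or analyses are needed.

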6.3. Treatment Compliance

The patient will be instructed to comply with the dosage and dosing regimen of study treatment. The Investigator or designated study-site personnel will maintain a log of all study drug dispensed and returned. Compliance to all study drug administration should be documented in the patients' source documents. Additionally, noncompliance can also be considered in the event a patient intentionally takes more study drug than prescribed. In the event a patient is noncompliant with study treatment, discontinuation of the patient may be considered after discussion between the Sponsor and Investigator.

6.4. Concomitant Medications and Therapies

6.4.1. Prohibited Concomitant Medications

Patients are not permitted to receive any other investigational or anticancer therapy, including chemotherapy, immunotherapy, biological response modifiers, or antineoplastic endocrine

therapy during the study treatment period (with the exception of permitted tumor therapies listed in Section 6.4.4).

Acid-reducing agents may have the potential to reduce TAS3351 plasma concentration and potentially the activity of TAS3351. The use of proton pump inhibitors (PPI) is prohibited for patients receiving TAS3351. For other acid reducing agents (ARAs), see Section 6.4.2.

6.4.2. Concomitant Medications and Therapies Requiring Precautions

Drug interaction studies have not been conducted in humans. The following information is based on results from in vitro studies. Caution is advised if these drugs (examples provided in Appendix A) are given concomitantly:

Potential effects of TAS3351 on other drugs:

- **CYP2C8, CYP2C9, and CYP2C19 substrates:** TAS3351 is a potential reversible inhibitor of CYP2C8, CYP2C9, and CYP2C19. Depending on achievable steady-state plasma TAS3351 concentrations, TAS3351 may increase the concentration and activity of CYP2C8, CYP2C9, and CYP2C19 substrates.
- **CYP3A substrates:** TAS3351 has the potential to time-dependently inhibit CYP3A. Depending on achievable steady-state plasma TAS3351 concentrations and doses, TAS3351 may increase the concentration and activity of CYP3A substrates.
- **CYP1A2 substrates:** TAS3351 is a potential inducer of CYP1A2. Depending on achievable steady-state plasma TAS3351 concentrations, TAS3351 may reduce the concentration and activity of CYP1A2 substrates.
- **P-gp and BCRP substrates:** TAS3351 is a potential inhibitor of P-gp and BCRP. Depending on achievable steady-state plasma TAS3351 concentrations and dose, TAS3351 may increase the concentration and activity of P-gp and BCRP substrates.

Potential effects of other drugs on TAS3351:

- **Strong and moderate inhibitors/inducers of CYP3A:** TAS3351 is a potential substrate of CYP3A metabolism. CYP3A inhibitors/inducers (see Appendix A) may increase/reduce the concentration and activity of TAS3351.

Strong or moderate CYP3A inhibitors inducers and medications known to prolong QTc interval or to be arrhythmogenic (such as ondansetron, erythromycin, droperidol; see also: <http://crediblemeds.org>) should be avoided or substituted with other concomitant therapies while receiving TAS3351, if possible. However, if concomitant use cannot be avoided, patients should be closely monitored for any potential AEs and TAS3351 dose modifications should be performed accordingly as outlined in Section 6.2. The Investigator may also consider a TAS3351 dose reduction while concomitant treatment with a strong or moderate CYP3A inhibitor is being administered (eg, ciprofloxacin for an infection).

Acid-reducing agents (ARAs) may have the potential to reduce TAS3351 plasma concentration and potentially the activity of TAS3351. As mentioned in Section 6.4.1, the use of proton pump inhibitors (PPI) is prohibited for patients receiving TAS3351. Concomitant use of other ARAs should be avoided whenever possible. If concomitant use of ARAs is unavoidable, staggered dosing of histamine H2 receptor antagonists (H2 blockers) (TAS3351

administered at least 2 hours before or at least 12 hours after administration of H2 blockers) or antacids (TAS3351 administered at least 2 hours before or at least 2 hours after antacids) is recommended. Caution is advised with concomitant administration of ARAs with TAS3351.

6.4.3. Permitted Concomitant Medications

Local or regional palliative cryotherapy or radiation, such as for bone pain or palliative surgery (non-antineoplastic intent), are permitted (provided the target lesion is not a site of measurable disease and is not indicative of disease progression). If extended field radiation therapy or palliative radiation to a focal site of measurable disease is deemed to be in the best interest of the patient following discussion between the Investigator and the Sponsor, the patient will be censored for the primary analysis of efficacy. Study therapy should be ceased a minimum of 2 days prior to administration of palliative treatment and may be resumed 7 days after the procedure or when the patient has recovered from the side effects of the procedure. Moreover, endocrine therapy for controlled prostate or breast cancer is permitted, if approved by the treating physician. Patients are allowed to receive COVID-19 vaccination while being on study.

